2.7.1 Secondary endpoints

The secondary efficacy endpoint is the proportion of subjects aged 45 to 55 years achieving 75 or more ETDRS letters in binocular DCNVA at Month 3.

2.7.2 Statistical hypothesis, model, and method of analysis

The analysis of the secondary efficacy endpoint is based on the data observed in the FAS population, according to the treatment group subjects was randomized and the DCNVA stratum that was assigned at randomization. The comparison between the two treatment groups will be performed using stratified Cochran-Mantel-Haenszel (CMH) test at one-sided 5% level of significance, with stratified baseline DCNVA and age group as the stratification factors. Alternatively, if the cell count for any of the strata is too small (e.g., <5), the analysis will be done separately for each of the two stratification factors.

Assuming the following hypotheses will be tested:

$$H_0: \delta_2 = 0 \text{ vs. } H_a: \delta_2 > 0$$

where δ_2 is the difference of proportion of subjects achieving 75 or more ETDRS letters in binocular DCNVA between the UNR844-CI and placebo at Month 3.

2.7.3 Handling of missing values/censoring/discontinuations

The estimand for the secondary efficacy endpoint is closely related to the estimand for the primary efficacy endpoint (refer to [Section 2.5.3](#)). For subjects who has a DCNVA assessment at Month 3 and do not have intercurrent event (as defined in [Section 2.5.1](#)), the observed letter score will be used to derive the endpoint of achieving 75 or more ETDRS letters or not. For subjects who has no DCNVA assessment at Month 3 or have intercurrent event ([Section 2.5.1](#)), the predicted value of the estimand for the primary efficacy endpoint will be used to derive the endpoint of achieving 75 or more ETDRS letters or not.

2.8 Safety analyses

For all safety analyses, the SAF will be used. All listings and tables will be presented by treatment group.

2.8.1 Adverse events (AEs)

Summary tables for AEs and SAEs will summarize only on-treatment events, with a start date during the on-treatment period (TEAEs and TESAEs, respectively). The on-treatment period lasts from the date of first administration of study treatment to 30 days after the date of the last actual administration of any study treatment ([Section 2.1.1.5](#)).

The secondary endpoint for safety is the frequency of TEAEs and TESAEs in all subjects.

The number (and proportion) of subjects with TEAE will be summarized for ocular and non-ocular AEs separately, by treatment group and overall in the following ways:

- Overall summary of subjects with any TEAE, any severe TEAE, any study drug related TEAE, any TEAE leading to study drug discontinuation, any TESAE, any study drug related TESAE
- TEAE by primary system organ class and preferred term
- TEAE by primary system organ class, preferred term and maximum severity
- TESAE by primary system organ class and preferred term
- Study drug related TESAE by system organ class and preferred term
- TEAE leading to study drug discontinuation by primary system organ class and preferred term
- TEAE leading to study drug interruption by primary system organ class and preferred term

Except for the first table, all the above AE summaries will be provided by descending frequency in the UNR844-CI group. A subject with multiple adverse events within a primary system organ class is only counted once towards the total of the primary system organ class.

Any other AEs or SAEs will be listed.

All these analyses will be based on the most updated MedDRA version available prior to the database lock.

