5. Action taken regarding with study treatment. All adverse events must be treated appropriately. Treatment may include one or more of the following:
  - dose not changed
  - drug interrupted/withdrawn
6. Its outcome (i.e., its recovery status or whether it was fatal)

Conditions that were already present at the time of informed consent should be recorded in medical history of the subject.

Adverse events (including lab abnormalities that constitute AEs) should be described using a diagnosis whenever possible, rather than individual underlying signs and symptoms.

Adverse event monitoring should be continued for at least 30 days (or end of study visit, whichever is longer) following the last dose of study treatment.

Once an adverse event is detected, it must be followed until its resolution or until it is judged to be permanent (e.g., continuing at the end of the study), and assessment must be made at each visit (or more frequently, if necessary) of any changes in severity, the suspected relationship to the study treatment, the interventions required to treat it, and the outcome.

Information about adverse drug reactions for the investigational drug can be found in the IB.

[figure not shown]
Abnormal laboratory values or test results constitute AEs only if they fulfill at least one of the following criteria:

- They induce clinical signs or symptoms
- They are considered clinically significant
- They require therapy

Clinically significant abnormal laboratory values or test results must be identified through a review of values outside of normal ranges/clinically notable ranges, significant changes from baseline or the previous visit, or values, which are considered to be non-typical in subjects with the underlying disease.

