### **10.1.2 Serious adverse events**

A SAE is defined as any AE [appearance of (or worsening of any pre-existing)] undesirable sign(s), symptom(s) or medical condition(s) which meets any one of the following criteria:

- Fatal
- Life-threatening
  - Life-threatening in the context of a SAE refers to a reaction in which the subject was at risk of death at the time of the reaction; it does not refer to a reaction that hypothetically might have caused death if it were more severe (please refer to the ICH-E2D Guidelines).
- Results in persistent or significant disability/incapacity
- Constitutes a congenital anomaly/birth defect
- Requires inpatient hospitalization or prolongation of existing hospitalization, unless hospitalization is for:
  - Routine treatment or monitoring of the studied indication, not associated with any deterioration in condition
  - Elective or pre-planned treatment for a pre-existing condition that is unrelated to the indication under study and has not worsened since signing the informed consent
  - Social reasons and respite care in the absence of any deterioration in the subject's general condition
  - Treatment on an emergency outpatient basis for an event not fulfilling any of the definitions of a SAE given above and not resulting in hospital admission
- Is medically significant (i.e., defined as an event that jeopardizes the subject or may require medical or surgical intervention to prevent one of the outcomes listed above)

Medical and scientific judgment should be exercised in deciding whether other situations should be considered serious reactions, such as important medical events that might not be immediately life threatening or result in death or hospitalization but might jeopardize the subject or might require intervention to prevent one of the other outcomes listed above. Such events should be considered as “medically significant”. Examples of such events are intensive treatment in an emergency room or at home for allergic bronchospasm, blood dyscrasias or convulsions that do not result in hospitalization or development of dependency or abuse.

[figure not shown]
All malignant neoplasms will be assessed as serious under “medically significant” if other seriousness criteria are not met

Any suspected transmission via a medicinal product of an infectious agent is also considered a serious adverse reaction.

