### **10.1.3 SAE reporting**

To ensure subject safety, every SAE, regardless of causality, occurring after the subject has provided informed consent and until 30 days following the last administration of study treatment must be reported to Novartis Safety within 24 hours of learning of its occurrence. Detailed instructions regarding the submission process and requirements are to be found in the investigator site file provided to each site.

All follow-up information for the SAE including information on complications, progression of the initial SAE and recurrent episodes must be reported as follow-up to the original episode within 24 hours of the investigator receiving the follow-up information. An SAE occurring at a different time interval or otherwise considered completely unrelated to a previously reported one must be reported separately as a new event.

If the SAE is not previously documented in the IB (i.e., a new occurrence) and is thought to be related to the study treatment, a Novartis Safety Department associate may urgently require further information from the investigator for health authority reporting. Novartis may need to issue an Investigator Notification to inform all investigators involved in any study with the same study treatment that this SAE has been reported.

Suspected Unexpected Serious Adverse Reactions (SUSARs) will be collected and reported to the competent authorities and relevant ethics committees as per national regulatory requirements in participating countries.

Any SAEs experienced after the 30-day period following the last administration of study treatment should only be reported to Novartis Safety if the investigator suspects a causal relationship to study treatment.

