### **12.5.2 Safety endpoints**

For all safety analyses, the safety set will be used. All listings and tables will be presented by treatment group.

Summary tables for AEs will summarize only on-treatment events, with a start date during the on-treatment period (TEAEs). The on-treatment period lasts from the date of first administration of study treatment to 30 days after the date of the last actual administration of any study treatment.

The secondary endpoint for safety is the frequency of TEAEs and TESAEs in all subjects.

The number (and proportion) of subjects with TEAE will be summarized in the following ways:

[figure not shown]
[figure not shown]
- Overall summary of subjects with any TEAE, any severe TEAE, any study drug related TEAE, any TEAE leading to study drug discontinuation, any TESAE, any study drug related TESAE
- TEAE by primary system organ class and preferred term
- TEAE by descending frequency and preferred term for ocular and non-ocular respectively
- TEAE by maximum severity
- TESAE by primary system organ class and preferred term
- Study drug related TESAE by system organ class and preferred term

[figure not shown]
Any other AEs or SAEs will be listed.

A subject with multiple adverse events within a primary system organ class is only counted once towards the total of the primary system organ class.

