2.1.1.5 On-treatment period

The on-treatment period lasts from the date of first administration of study treatment to 30 days after the date of the last actual administration of any study treatment, i.e., date of the last actual administration of any study treatment (from 'Study treatment' CRF) – date of first administration of study treatment (from 'Study treatment' CRF) +1 + 30.

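### Treatment-emergent AEs and SAEs are defined by start date alone, so an event that begins between consent and first dose and worsens on study drug may drop out of the secondary safety endpoint

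*SAP*

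**What the plan says.** SAP 2.8.1 restricts the AE and SAE tables: they "will summarize only on-treatment events, with a start date during the on-treatment period". Protocol 12.5.2 sets the same condition. SAP 2.1.1.5 fixes the window: "The on-treatment period lasts from the date of first administration of study treatment to 30 days after the date of the last actual administration". The endpoint inherits the rule, because SAP 2.8.1 states: "The secondary endpoint for safety is the frequency of TEAEs and TESAEs in all subjects". The tables of maximum severity, of events leading to discontinuation and of events leading to interruption are built from the same TEAEs. Anything outside the rule is listed, not tabulated.

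Collection begins earlier than the window. Protocol 10.1.1 defines an AE from written informed consent onward, and Table 8-1 marks AE collection at screening (Day -7) and at baseline (Day 1). Each AE is recorded with start and end dates, a severity grade and whether it is serious. Once an AE is detected, "assessment must be made at each visit (or more frequently, if necessary) of any changes in severity".

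**The concern.** Treatment emergence normally covers two things: events that begin on drug, and events that were already present and get worse on drug. The plan's definition covers only the first. If an AE that began in the screening week stays on one record with one start date, an increase in severity on study drug leaves that date unchanged, and the event never becomes a TEAE. If it becomes serious, it never becomes a TESAE.

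The secondary safety endpoint is the frequency of exactly these two categories. Related outputs could also disagree. Suppose such an event worsened and led the subject to stop treatment. The subject would be counted under adverse event in the summary of reasons for treatment discontinuation (SAP 2.4.1), and later data would be imputed by CIR under SAP 2.5.3. The event would still be absent from the table of TEAEs leading to discontinuation.

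**Working it through.** The plan gives no figure for this point, so there is nothing to reproduce. The check is a reading of the sections together, followed by a rough sizing.

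**Reading the sections together**

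| Question | Where | Answer |
|---|---|---|
| When does AE collection start? | Protocol 10.1.1, Table 8-1 | At consent, before first dose |
| What makes an event treatment-emergent? | Protocol 12.5.2, SAP 2.8.1 | Start date in the on-treatment period |
| When does that period start? | SAP 2.1.1.5 | Date of first administration |
| Is there a clause for worsening or becoming serious? | Protocol 12.5.2, SAP 2.8.1 | No |
| Are changes in severity followed? | Protocol 10.1.1 | Yes, at each visit, for an AE already detected |
| Does a worsening get a new record or a new date? | Both documents | Not stated |
| Do the date-imputation rules help? | SAP 5.1.1.2 | No; they complete partial dates and do not address worsening |

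For an AE with onset between consent and first dose, the outcome depends on the unanswered question. If the worsening is entered as a new dated record, the start-date rule counts it. If the existing record is updated, the rule leaves it out.

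**Size of the window.** Dosing lasts 90 days, so the on-treatment period is 90 + 30 = 120 days. With 7 days before first dose, the pre-dose share of AE collection time is 7 / (7 + 120) = 5.5%. If screening took 14 days (assumed), it is 14 / (14 + 120) = 10.4%.

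**Expected number of subjects.** Let q be the probability that a subject has an AE starting before first dose, and w the probability that it then worsens on drug. The documents give neither. The expected number is 120 × q × w.

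- Low: q = 2%, w = 5%: 120 × 0.02 × 0.05 = 0.12
- Middle: q = 5%, w = 20%: 120 × 0.05 × 0.20 = 1.2
- High: q = 10%, w = 20%: 120 × 0.10 × 0.20 = 2.4

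**A second route to q.** Assume that a proportion p of subjects has an AE over three months (13 weeks) at a constant rate. The one-week probability is 1 − exp(ln(1 − p) / 13).

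- p = 0.30: 2.7%, or 3.2 of 120 subjects
- p = 0.60: 6.8%, or 8.2 of 120 subjects

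If 10% to 20% of these worsen, the range is 3.2 × 0.10 = 0.3 to 8.2 × 0.20 = 1.6 subjects. This route probably runs high, because it applies a rate seen over treatment to an untreated week.

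**Any-TEAE row.** That row counts subjects, so anyone with another TEAE is already in it. Assuming independence, multiply by the share without another TEAE (1 − p): 0.3 × 0.7 = 0.2, and 1.6 × 0.4 = 0.6. The any-TEAE row would miss less than one subject.

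**The case against.** The strongest objection is that the omission depends on an eCRF convention that the documents do not show. The follow-up duty in Protocol 10.1.1 tells investigators what to assess; it does not say how records are structured or dated. If sites open a new record when an event worsens, the existing rule already counts it. This stands. It is why the conclusion is that such events may be left out. A reader might infer that the documents establish the omission, and they do not. What remains is that the endpoint depends on an unstated convention that sites could apply differently.

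Three further inferences are tempting and are not supported.

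- **Recurrences.** Protocol 10.1.3 says that "progression of the initial SAE and recurrent episodes must be reported as follow-up to the original episode", which might suggest that a recurrence on drug keeps a pre-dose date. That section covers SAE reporting to the sponsor's safety department, and its next sentence makes an SAE at a different time interval a separate new event. It says nothing about non-serious AEs. The point here does not rely on recurrence.
- **Conditions present at consent.** Protocol 10.1.1 sends these to medical history. Their worsening on drug could be entered as a first AE record with an on-treatment date and so be counted. Protocol 10.1.2 also treats worsening of something pre-existing as capable of being an event in itself. Only onset between consent and first dose is at issue.
- **Direction.** A reader might conclude that the start-date rule can only undercount. It works by calendar date, so a Day 1 event that precedes the first drop counts as a TEAE. Where treatment start is the reference date, SAP 5.1.1.2 can also set an uncertain start to the day after treatment start, which adds TEAEs.

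It is also fair to say that the rule is the same in both masked arms, that no bias between arms has been shown, and that the excluded events remain visible in listings.

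**Conclusion.** The point holds as a gap in the definition, of minor importance. Both documents make treatment emergence depend on start date alone, and neither says how a worsening is dated. An AE that starts between consent and first dose and then increases in severity or becomes serious on study drug may therefore be missing from the secondary safety endpoint and from the severity and discontinuation tables.

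The size is about 0.1 to 2.4 of 120 subjects across both arms, and below one subject in the any-TEAE row. These figures rest on assumed rates of pre-dose onset and of worsening. They support only the statement that the number is small.

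One subject would matter mainly in sparse rows. In the prior study, ocular terms reported at 4% to 6% of 50 treated subjects amount to 2 to 3 subjects each, and there were no SAEs (Protocol 1.1 and 4.5). One omitted case would be noticeable there, although a screening-week AE that turns serious on drug is unlikely.

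**What to change.** 1. In SAP 2.8.1 and Protocol 12.5.2, define a TEAE (TESAE) as an AE (SAE) that starts, or that increases in severity or becomes serious, on or after first administration and within 30 days of the last.
2. In the maximum-severity table, use the highest severity recorded in the on-treatment period.
3. In the eCRF guidance, state that a worsening of an event that began before first dose is entered with its own date. Without that date the definition in step 1 cannot be programmed.

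The cost is one clause in each document, one derivation rule and one line of site guidance. The downside is that the TEAE count may rise by a subject or two.

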2.8.1.1 Adverse events of special interest / grouping of AEs

Not applicable.

2.8.2 Deaths

Death will not be individually listed, or tabulated, but will be included as part of the AE analyses.

2.8.3 Laboratory data

It is not applicable, as data will only be recorded in the source document.

2.8.4 Other safety data

2.8.4.1 ECG and cardiac imaging data

It is not applicable, as data will only be recorded in the source document.

2.8.4.2 Vital signs

All vital signs data (including systolic/diastolic blood pressure (BP), and heart rate measurements) will be listed by treatment group, subject, and visit/time. Summary statistics (n, mean, median, standard deviation, min, max) for the absolute value and the change from baseline will be provided by treatment and visit/time.

2.9 Pharmacokinetic endpoints

[figure not shown]
Not applicable.

[figure not shown]
2.10 PD and PK/PD analyses

[figure not shown]
Not applicable.

2.11 Biomarkers

Not applicable.

2.13 Interim analysis

Not applicable.

[figure not shown]
3 Sample size calculation

3.1.1 Primary endpoint

Assuming a mean difference of 4.9 ETDRS letters with a common standard deviation of 6.02 ETDRS letters in change from baseline in binocular DCNVA at 3 months between UNR844 and placebo, based on the results of the prior study in presbyopic subjects, 66 subjects (33 in each arm) aged 45 to 55 years are required to complete the study to achieve an approximate power of 94% at 5% (one-sided) significance level. Assuming about 90% subjects will complete the study, a total of 72 subjects for the primary efficacy endpoint will be enrolled.

3.1.2 Secondary endpoints

Assuming the proportion of subjects achieving 75 or more ETDRS letters in binocular DCNVA at Month 3 are 40.5% and 10.5% for UNR844-CI and placebo, respectively, based on the results of the prior study in presbyopic subjects, 66 subjects (33 in each arm) aged 45 to 55 years are required to be completed to achieve an approximate power of 82% at 5% (one-sided) significance level.

4 Change to protocol specified analyses

Not applicable.

5 Appendix

Statistical methods are described in the main part of the clinical study report. This appendix provides further details on the statistical derivation and practical implementation.

5.1 Imputation rules of missing dates

The general approach to handling missing dates is shown below for dates of AEs, medical history diagnosis, and concomitant treatment. The imputation of missing dates for surgery or procedures will use the same rules as for concomitant treatment.

The detailed algorithms will appear in Programming Dataset Specifications.

For the purpose of date imputation, the treatment follow up period date is defined as the last available visit date.

5.1.1 AE date imputation

5.1.1.1 Adverse event end date imputation

1. If the AE end date month is missing, the imputed end date should be set to the earliest of the (treatment follow up period date, 31DECYYYY, date of death, cut-off date if available).

2. If the AE end date day is missing, the imputed end date should be set to the earliest of the (the last visit date, last day of the month, date of death, cut-off date if available).

3. If AE year is missing or AE is ongoing, the end date will not be imputed.

4. In case the imputed AE end date is before AE start date, then use AE start date as imputed AE end date.

5.1.1.2 Adverse event start date imputation

The following table explains the notation used in the logic matrix. Please note that **missing start dates** will not be imputed.

	Day	Month	Year
Partial Adverse Event Start Date	Not used	MON	YYYY
Treatment Start Date	Not used	TRTM	TRTY

The following matrix explains the logic behind the imputation.

	MON MISSING	MON < TRTM	MON = TRTM	MON > TRTM
YYYY MISSING	(1) No convention	(1) No convention	(1) No convention	(1) No convention
YYYY < TRTY	(2.a) Before Treatment Start	(2.c) Before Treatment Start	(2.c) Before Treatment Start	(2.c) Before Treatment Start
YYYY = TRTY	(4.a) Uncertain	(4.c) Before Treatment Start	(4.d) Uncertain	(4.d) After Treatment Start
YYYY > TRTY	(3.a) After Treatment Start	(3.c) After Treatment Start	(3.c) After Treatment Start	(3.c) After Treatment Start

Before imputing AE start date, find the AE start reference date.

1. If the (imputed) AE end date is complete and the (imputed) AE end date < treatment start date then AE start reference date = min (informed consent date, earliest visit date).
2. Else AE start reference date = treatment start date

Impute AE start date -

1. If the AE start date year value is missing, the date uncertainty is too high to impute a rational date. Therefore, if the AE year value is missing, the imputed AE start date is set to NULL.
2. If the AE start date year value is less than the treatment start date year value, the AE started before treatment. Therefore:
 - a. If AE day and month are missing, the imputed AE start date is set to the mid-year point (01JulYYYY).
 - b. If AE month is missing but day is not missing, the observed start date will be used with month imputed as JulYYYY.
 - c. Else if AE month is not missing, the imputed AE start date is set to the mid-month point (15MONYYYY).
3. If the AE start date year value is greater than the treatment start date year value, the AE started after treatment. Therefore:
 - a. If the AE day and month are missing, the imputed AE start date is set to the year start point (01JanYYYY).
 - b. If AE month is missing but day is not missing, the observed start date will be used with month imputed as JulYYYY.
 - c. Else if the AE month is not missing, the imputed AE start date is set to the later of (month start point (01MONYYYY), AE start reference date + 1 day).
4. If the AE start date year value is equal to the treatment start date year value:
 - a. And the AE day and month are missing the imputed AE start date is set to the AE reference start date + 1 day.

- b. If AE month is missing and day is not missing, the observed start date will be used with month imputed as the reference start month.
- c. Else if the AE month is less than the treatment start month, the imputed AE start date is set to the mid-month point (15MONYYYY).
- d. Else if the AE month is equal to the treatment start date month or greater than the treatment start date month, the imputed AE start date is set to the later of (month start point (01MONYYYY), AE start reference date + 1 day).

If complete (imputed) AE end date is available and the imputed AE start date is greater than the (imputed) AE end date, then imputed AE start date should be set to the (imputed) AE end date.

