### 6.1.4 Treatment duration

The planned treatment duration is three months.

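### An adverse event with a missing start year gets a NULL start date, so under the SAP as written it cannot enter any TEAE or TESAE table, even if it is ongoing or ended after first dose

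*SAP*

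**What the plan says.** SAP 5.1.1.2 rule 1 covers AE records with no start year. It reasons that "the date uncertainty is too high to impute a rational date" and concludes that "if the AE year value is missing, the imputed AE start date is set to NULL". The logic matrix above it gives no convention for a missing year in any month column, so a recorded month is not used either.

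SAP 2.8.1 then states: "Summary tables for AEs and SAEs will summarize only on-treatment events, with a start date during the on-treatment period". Protocol 12.5.2 sets the same test for AEs. The window is defined in SAP 2.1.1.5: "The on-treatment period lasts from the date of first administration of study treatment to 30 days after the date of the last actual administration". All remaining AEs and SAEs are listed.

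The frequency of TEAEs and TESAEs in all subjects is the secondary safety endpoint (Protocol Table 2-1, SAP Table 1-1).

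Before its numbered rules, SAP 5.1.1.2 derives an AE start reference date. This is the earlier of consent and first visit if a complete end date precedes treatment start, and treatment start otherwise. Rule 4.a covers a start year equal to the treatment year with day and month missing; there "the imputed AE start date is set to the AE reference start date + 1 day".

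**The concern.** A NULL date cannot satisfy a test that requires a start date inside a window, and neither document gives a fallback for NULL dates. An event whose record shows that it was present during treatment, because it ended after first dose or is still ongoing, is then handled in the tables as if it were not treatment-emergent. Nothing in the record supports that.

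The effect on the safety endpoint runs one way, because absolute TEAE and TESAE frequencies can fall but not rise. A serious event of this kind would be missing from the TESAE tables and visible only in a listing.

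The section is also inconsistent. Its reference date already separates events that ended before treatment from all others. Rule 4.a uses that date and defaults to on-treatment, while rule 1 ignores it. For concomitant medication, SAP 5.1.2.2 does impute a date when the start year is missing.

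**Working it through.** The plan gives no figure on this point, so there is none to reproduce. The check traces the rules and then counts days.

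**1. Two ongoing events traced through the SAP**

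| Step | Start date wholly missing | Start year known (treatment year), day and month missing |
|---|---|---|
| End date (5.1.1.1) | Ongoing, not imputed | Ongoing, not imputed |
| Reference date (5.1.1.2) | Treatment start | Treatment start |
| Start date | NULL (rule 1) | Treatment start + 1 day (rule 4.a) |
| TEAE table (2.8.1) | No | Yes |
| Listing | Yes | Yes |

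**2. Share of the AE collection window that is on treatment**

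Inputs:
- Collection starts at consent (Protocol 10.1.1). Conditions already present at consent go to medical history, so a recorded AE should not predate it.
- Screening is Day -7 (Protocol Table 8-1), and SAP Table 2-1 gives its window as Day -7 to Day -1, which is 7 days.
- "The planned treatment duration is three months" (Protocol 6.1.4), and the Month 3 visit is Day 90.
- Monitoring continues for at least 30 days after last dose, or to the end-of-study visit if that is later (Protocol 10.1.1).

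On-treatment days = last dose − first dose + 1 + 30 = 90 − 1 + 1 + 30 = 120. Collection days = 7 + 120 = 127. Share = 120/127 = 94.5%.

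Variations (the longer screening periods and the Day 14 stop are assumptions):

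| Case | On-treatment / collection days | Share |
|---|---|---|
| 14 screening days, treated to Day 90 | 120/134 | 89.6% |
| 28 screening days, treated to Day 90 | 120/148 | 81.1% |
| Treatment stops Day 14, collection ends 30 days later | 44/51 | 86.3% |
| Treatment stops Day 14, followed to Day 90 | 44/97 | 45.4% |

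**3. What a missing year leaves unknown**

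The same calendar month in two different years lies about eleven months apart, so a 127-day window cannot contain both. A recorded month therefore fixes the year and leaves at most 31 candidate days. A rule 4.a record can have up to 127 candidate days and is still dated on treatment.

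If window start dates are spread evenly over a 365-day year, the whole window lies in one calendar year for 365 − 127 + 1 = 239 of them. As 239/365 = 65%, in about two thirds of cases the year would add no information even to a wholly missing date.

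**4. Size per affected subject**

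About 120 subjects randomized 1:1 give 60 per arm, and 1/60 = 1.7 percentage points on any one TEAE rate. The number of records without a start year cannot be derived from the documents.

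**The case against.** The strongest answer is that hardly any record will lack a start year. The study lasts about three months, AEs are sought at every visit, the start date is a required AE item as far as possible, and missing values are queried (Protocol 10.1.1, 11.2). SAEs must be reported within 24 hours, and their documentation is fully verified by monitors (Protocol 10.1.3, 11.3). This stands, and it keeps the point minor.

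Rule 1 is also a prespecified choice with a stated reason, and SAP 5.1 leaves detailed algorithms to programming specifications that are not available here. So the exclusion is shown only for the SAP as written. But rule 1 is explicit, and a specification that classified these events otherwise would be adding a rule that the SAP lacks.

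A reader might infer more than the documents support:
- *That the rule makes UNR844 look safer than placebo.* It is identical in both arms of a double-masked trial, and the safety endpoint is descriptive. Only absolute undercounting follows.
- *That 94% of undated events are misclassified.* The figure is a share of days for a subject treated to Day 90. It would be a share of events only with uniform onset.
- *That rule 4.a accepts vaguer records than rule 1 rejects.* This is true only against records with a known month. Against a wholly missing date, rule 4.a records are equally or better located.
- *That the whole section defaults to on-treatment.* Rule 4.c gives a pre-treatment date, 4.b can do so, and 3.b can fall outside the period. The contrast is with 4.a, and with 4.d when the month is the treatment-start month.
- *That the events are lost.* They are listed.

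**Conclusion.** The point holds for the SAP text. An AE or SAE with no start year cannot be counted as treatment-emergent, whatever its end date or ongoing status shows, and this conflicts with the default in rule 4.a. The consequence is possible undercounting of absolute TEAE and TESAE frequencies in both arms, at 1.7 percentage points per affected subject in an arm of 60.

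On-treatment is the more plausible default for most subjects. It covers about 94% of collection days for a subject with 7 screening days and treatment to Day 90, and 81% to 90% with 28 or 14 screening days. It is not safe for everyone: the share is 45% for a subject who stops at Day 14 and is followed to Day 90.

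The number of affected events is unknown and probably very small. This is a minor point, worth making because the correction is cheap. It is not evidence that the safety comparison is biased.

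**What to change.** Replace rule 1 in SAP 5.1.1.2 with two cases:

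- **Year missing, month recorded.** Take the year from the subject's window from consent to last contact, then apply rules 2 to 4 where the date is still incomplete. This respects a recorded month before treatment start, which a blanket imputation to the day after first dose would override.
- **Year and month both missing.** Classify the event as treatment-emergent, with start date = AE start reference date + 1 day, capped at the end date as the section already provides, unless a complete end date precedes first dose. In that case the event stays pre-treatment.

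Align the sentence in the same section that rules out imputing missing start dates, update the missing-year row of the matrix, and carry both cases into the programming specification. Flag the affected records in the AE listing.

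The cost is a few lines of text and code. The downside is a small possible overcount of TEAEs, for example an onset between consent and first dose, or one more than 30 days after an early last dose. The flag lets a reader see how many counts rest on the default.
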